9.3 Primary Endpoint(s) Analysis

9.3.1 Definition of endpoint(s)

The primary endpoints are defined as follows:

- Maximum concentration, C_{max}
- Area under the curve from 0 to the time of the last quantifiable concentration, $AUC_{(0-t)}$

9.3.2 Main analytical approach

The bioavailability of BRV dry syrup (1.25g of granules for oral solution 4% w/w, corresponding to 50mg of BRV) (test) will be compared with BRV 50mg dose administered as a 50mg tablet (reference).

The parameters C_{max} and $AUC_{(0-t)}$ will be evaluated according to a univariate model of analysis of variance, adapted to crossover experimental designs. The model will include the treatment (tablet or dry syrup), the dosing period, and treatment sequence as fixed effects. The study participant (nested to the sequence) will be the random effect. The dependent variables will be logarithmically transformed by natural logarithms (\ln) prior to statistical testing, following the usual recommendations.

This linear mixed model is represented as:

$$\log(Y_{ijkl}) = \mu + S_{i(j)} + Q_j + F_k + P_l + e_{ijkl}, \text{ where}$$

- $\log(Y_{ijkl})$ is the log transformed PK parameter value of the i -th subject ($i=1,2,3,..$) in the j -th sequence ($j=1,2$); for the k -th treatment ($k=1,2$) in the l -th period ($l=1,2$),
- μ is the overall mean,
- $S_{i(j)}$ is the random effect of the i -th subjects nested to the j -th sequence,
- Q_j is the fixed effect for the j -th sequence,
- F_k is the fixed effect for the k -th treatment,
- P_l is the fixed effect for the l -th period,
- e_{ijkl} is the (residual) random error in observing $\log(Y_{ijkl})$.

The MIXED procedure in SAS software will be used for this analysis.

For estimation based on a linear mixed model, covariance matrix applied to the within-subject error will be estimated by restricted maximum likelihood (REML). The Kenward-Roger

approximation will be used to estimate the degree of freedom. Variance component structure will be used as covariance in this linear mixed model.

The adjusted test/reference geometric mean ratio and its corresponding 90% confidence intervals (CIs) will be calculated. Bioequivalence between the test (dry syrup) and reference (tablet) formulations will be concluded if the 90% CI limits for C_{max} and $AUC_{(0-t)}$ fall fully within 80% to 125%.

Inter-participant and intra-participant variability for each parameter will also be derived from these analyses as geoCVs.

Geometric least squares means and the corresponding 90% CI for each treatment (tablet or dry syrup) will be provided as well.

9.4 Other Endpoint(s) Analysis

9.4.1 Definition of endpoint(s)

The other PK endpoints are defined as follows:

- Area under the curve from 0 to infinity, AUC
- Extrapolated AUC, AUC_{extr}
- Total clearance after oral administration, CL/F
- Apparent volume of distribution, V_z/F
- Mean residence time (i.e., of the unchanged drug in the systemic circulation), MRT
- Time of C_{max} , t_{max}
- Terminal elimination half-life, $t_{1/2}$
- First order terminal elimination rate constant, λ_z

9.4.2 Main analytical approach

AUC will be analyzed using the same linear mixed model as in primary endpoints (see Section 9.3.2).

The adjusted test/reference geometric mean ratio and the corresponding 90% CI will be calculated.

Inter-participant and intra-participant variability for each parameter will also be derived from analyses using the linear mixed model as geoCVs. Geometric least squares means and the corresponding 90% CI for each treatment (tablet or dry syrup) will be provided as well.

For t_{max} , a distribution-free 90% CI using Hodges-Lehmann's method will be calculated for the median differences (location shift) between each test and the reference. Median and the corresponding 90% CI for each treatment (tablet or dry syrup) will be provided using cumulative

binomial probability. If the exact Hodges-Lehmann confidence limits cannot be calculated, asymmetric limits will be derived instead of symmetric limits.

10 SAFETY ANALYSES

Unless otherwise specified, all summaries will be based on the SS.

10.1 Extent of Exposure

Administration of IMP will be listed by treatment sequence, and Dosing Period for all participants in the SS and will include the following information: IMP formulation, date/ time of IMP administration.

10.2 Adverse Events

All AEs will be coded using the Medical Dictionary for Regulatory Activities (MedDRA®) and characterized as pretreatment and treatment emergent according to the intake of the IMP.

Adverse events with a start date prior to the first dose of IMP will be defined as pre-treatment AEs. A TEAE is defined as any AE with a start date/time on or after the first dose of IMP or any unresolved event already present before administration of IMP that worsens in intensity following exposure to IMP.

Imputed dates will not be shown in the listings; all dates will be displayed as reported in the database.

The following rules will be applied for partial start dates and time:

- If only the month and year are specified and the month and year of the first dose of IMP is not the same as the month and year of the start date, then use the 1st of the month, or the date of Screening if this is later (if the latter imputation results in an end date that is earlier than the start date, then use the 1st of the month). If time is missing this will be imputed as 00:00 h
- If only the month and year are specified and the month and year of the first dose of IMP is the same as the month and year of the start date, then use the date of the first dose of IMP. If this results in an imputed start date that is after the specified end date, then use the 1st of the month, or the date of Screening if this is later (if the latter imputation results in an end date that is earlier than the start date, then use the 1st of the month). If the imputed date is the date of dosing then time will be imputed as the start time of the dosing (i.e., event will be regarded as treatment-emergent)
- If only the year is specified, and the year of the first dose of IMP is not the same as the year of the start date then January 01 will be used. If time is missing this will be imputed as 00:00 h
- If only the year is specified, and the year of the first dose of IMP is the same as the year of the start date, then the date of the first dose of IMP will be used. If this results in an imputed start date that is after the specified end date, then January 01, or the date of Screening if this is later will be used (if the latter imputation results in an end date that is earlier than the start date, then January 01 will be used). If the imputed date is the date of

first dose of IMP then time will be imputed as the start time of the study medication intake (i.e., event will be regarded as treatment-emergent)

- If the start date is completely unknown, then use the date of dosing. If this results in an imputed start date that is after the specified end date, then use January 01 of the year of the end date, or the date of Screening if this is later.

The following rules will be applied for partial stop dates:

- If only the month and year are specified, then use the last day of the month
- If only the year is specified, then use December 31 of the known year
- If the stop date is completely unknown, do not impute the stop date

Missing or partially missing date and/or times will be imputed as described in [Table 10-1](#) for the calculation of duration of each AE. AE duration is computed and reported in day and time format.

Table 10-1: Calculation Rules for Duration of AEs

Data Availability	Onset Date/Time	Outcome Date/Time	Calculation Rules
Complete data	D1/T1	D2/T2	Duration = $(D2-D1)*24+(T2-T1)$
End time missing	D1/T1	D2/--	End time is substituted by time 23:59h (=23.98 in decimal format). Duration=<(D2-D1)*24+(23.98-T1)
Start time missing	D1/--	D2/T2	Onset time is substituted by 00:00h. Duration=<(D2-D1)*24+T2
Start and end time missing	D1/--	D2/--	Duration=<[(D2-D1)+1]*24
Start day and time missing	--/--	D2/T2	Duration=<(D2-D0)*24+(T2-T0) For a participant in the SS, D0 and T0 are the date and time of the first administration of study medication and for screen failures, D0 is the date of the Screening Visit date and T0=00:00h.
End day and time missing	D1/T1	--/--	If the stop date is missing, duration will not be calculated.
Start and end date missing	--/--	--/--	If the stop date is missing, duration will not be calculated.

The duration of each AE will be calculated as follows and will be presented in dd:hh:mm format where dd represent days, hh: hours, and mm: minutes:

$$\text{Duration of AE} = \text{End date/time of AE} - \text{Start date/time of AE}$$

Adverse events will be assigned to Dosing Periods, based on the onset date/ time of the AE. Assignment to Dosing Periods will be done after missing dates have been imputed as described

above. AE will be assigned to a treatment based on the treatment received in the Dosing Periods as follows:

- Dosing Period 1: the start date is on or after IMP administration in Dosing Period 1 and prior to IMP administration in Dosing Period 2.
- Dosing Period 2: the start date is on or after IMP administration in Dosing Period 2.

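### Do the partial-start-date rules in SAP 10.2 charge adverse events that began after dose 2 to the wrong formulation?

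*SAP*

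**What the plan says.** Protocol 9.4.1 leaves the attribution of adverse events to Dosing Periods to the SAP. SAP 10.2 first completes the start date:

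- Month and year known: if the month and year of the first dose "is the same as the month and year of the start date, then use the date of the first dose of IMP". If it "is not the same as the month and year of the start date, then use the 1st of the month", or Screening if that is later.
- Year known: if the year of the first dose "is the same as the year of the start date, then the date of the first dose of IMP will be used"; in any other year, January 1.
- Nothing known: "If the start date is completely unknown, then use the date of dosing". This sentence does not say which dose.

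If the completed start falls after the recorded end of the event, it is moved earlier.

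Period, and with it formulation, comes second: "Assignment to Dosing Periods will be done after missing dates have been imputed as described". Period 1 runs from dose 1 until dose 2. The other window is "Dosing Period 2: the start date is on or after IMP administration in Dosing Period 2". SAP 10.2.1 then tabulates TEAEs and treatment-emergent SAEs, the secondary endpoint, by formulation and overall.

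**The concern.** The rules are built to settle whether an event is treatment-emergent, and dose 1 is the natural default for that. In a two-dose crossover the same imputed date also settles which formulation gets the event, and for that question dose 2 matters. The error runs one way: post-dose-2 events can move to Period 1, and none move back.

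With 24 participants, one moved participant is 1/24 = 4.2 points. That can decide entry to the table of non-serious TEAEs above 5% in SAP 10.2.2, since 1/24 = 4.2% is out and 2/24 = 8.3% is in.

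Two smaller worries go with it. The rule for a wholly unknown start leaves the dose unnamed. The TEAE definition also admits "any unresolved event already present before administration of IMP that worsens in intensity following exposure to IMP", and the start date of such an event precedes both period windows.

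**Working it through.** **Inputs.** The doses are 7 to 10 days apart and the follow-up visit is n = 7 to 9 days after dose 2 (SAP 5.1.1.1.3). These windows reproduce the stated study duration: 2 + 7 + 7 + 1 = 17 days and 28 + 10 + 9 + 1 = 48 days. The plan gives no figure for partial dates. I assume dose dates uniform over a 365-day year and onset uniform over days 0 to n after dose 2.

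**Share moved to Period 1.** A month-only event with true onset on day k after dose 2 is placed correctly only if the first of some month lies between dose 2 and the onset, both included. That is k + 1 days, so the chance is 12(k + 1)/365. Averaged over k = 0 to n, the share moved is m = 1 − 12(n + 2)/730.

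- n = 7: 1 − 108/730 = 0.852
- n = 8: 1 − 120/730 = 0.836
- n = 9: 1 − 132/730 = 0.819

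For year-only dates there is one January 1 instead of twelve firsts, so the share is 1 − (n + 2)/730 = 0.988, 0.986 and 0.985. Direct enumeration over 365 first-dose dates gives the same values, and 0% of true Period 1 events moved to Period 2.

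**How firm the share is.** It depends on the calendar. With onset on days 0 to 9 it is 100% when dose 1 falls on days 1 to 9 or 26 to 31 of the month, but 49%, 39%, 32%, 24%, 26% and 45% for days 18 to 23. With onset over days 0 to 39, which only the extended SAE window in Protocol 8.3.1 allows, the month-only share is 36.8%.

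**Could the moved events have been placed?** There are three cases for a month-only event that truly began after dose 2:

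1. The onset month contains dose 1. Dose 2 lies between dose 1 and the onset, so it is in that month too, and both periods fit.
2. Dose 1 is in an earlier month and dose 2 is in the onset month. Unless dose 2 is on the 1st, the days from the 1st to dose 2 belong to Period 1, so both periods fit. If dose 2 is on the 1st, the rule gives Period 2.
3. The onset month follows the month of dose 2. Only Period 2 fits, and the rule gives Period 2.

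So no event that the partial date can place is misplaced under the date rule. The same reasoning holds for years. The end date adds nothing: if it precedes dose 2 the event is in Period 1, where the rule already puts it; if it does not, both periods stay open. If an imputed 00:00 on the day of dose 2 is compared with the dose time, the shares rise to 85% to 88% and 98.8% to 99.0%; the additional events are those where dose 2 falls on the 1st of the month (or on January 1).

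**Effect on the comparison.** Let the true incidences be pT (tablet) and pD (dry syrup), with 12 participants per sequence and no period effect. The tablet column expects 12[pT + m·pD + (1 − m)pT] events and the dry syrup column 12[pD + m·pT + (1 − m)pD]. Their difference is 24(1 − m)(pT − pD). Among month-only TEAEs, 15% to 18% of the true difference is retained. If these are a share q of all TEAEs, the retained share overall is 1 − q·m. For assumed q of 1%, 5% and 10% that is about 0.99, 0.96 and 0.92.

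**The alternative.** Suppose undecidable events are counted under both formulations. With dose gap g, a true Period 1 month-only event is undecidable with probability a1 = 1 − 12(g + 1)/730, from 0.868 (g = 7) to 0.819 (g = 10). For Period 2 events a2 = m. The difference retained is 1 − (a1 + a2)/2, from 1 − (0.868 + 0.852)/2 = 0.140 to 1 − (0.819 + 0.819)/2 = 0.181.

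**The case for a change.** The best case for a change is that the rule understates the Period 2 formulation within each sequence, on the secondary endpoint, by a convention that was never aimed at that question. The imputed dates do not appear in the listings. The Data Evaluation Meeting (Protocol 9.5, SAP 11.1.2) can look at missing values case by case, but it is not said to override a programmed rule. Counting under both formulations would at least understate neither, and it would match the cautious treatment of missing severity and causality in SAP 10.2.2.

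The description of the rule stands, and so does its direction. The remedy does not. Double counting recovers no more of the difference than the present rule, lets the columns exceed the overall count, and can itself push a term above 5%. It exchanges one descriptive convention for another. The undecidable events are already open to view, because the listing shows dates as reported alongside period and treatment.

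The unnamed dose is a slip of wording. The month-matching rule in the same section uses the same expression for the first dose, the medication rule in SAP 6.3 names the first dose, and for duration Table 10-1 says "D0 and T0 are the date and time of the first administration of study medication". A programmer would take dose 1.

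The worsening point turns on whether the eCRF opens a new record when an event worsens. The documents do not show this, so no defect can be claimed.

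**Conclusion.** No change is called for. The rule is a default for events whose recorded date fits either period, and nothing in the dates would place them better. The 82% to 85% is conditional on a month-only date and on evenly spread dose dates and onsets.

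Such dates should be few, although the documents give no frequency. Participants are confined from Day -1 to Day 3 of each period, and the Schedule of Activities has adverse events recorded at each visit. Discharge is about 2 days after dosing. Check-in for Period 2 is 6 to 9 days after dose 1 and follow-up is 7 to 9 days after dose 2, so the unobserved stretches last 9 − 2 = 7 days at most. Year-only onsets should be rarer still.

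If one TEAE in twenty were month-only, the formulation difference would keep about 96% of its size. With balanced sequences, which replacement within sequence (Protocol 6.3) supports, neither formulation gains. The safety tables are descriptive, and C_max and AUC(0-t) do not depend on these dates.

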- If the stop date is completely unknown, do not impute the stop date. In this case the medication will be assigned to all Dosing Periods subsequent to the medication start date.

Concomitant medications will be assigned to Dosing Periods, based on the time when the medication is taken. Assignment to Dosing Periods will be done after missing dates have been imputed as described above. Concomitant medications will be assigned to a treatment based on the treatment received in the Dosing Periods as follows:

- Dosing Period 1: the start or end date is on or after IMP administration in Dosing Period 1 and prior to IMP administration in Dosing Period 2
- Dosing Period 2: the start or end date is on or after IMP administration in Dosing Period 2.

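### SAP 6.3 leaves a medication that spans both doses out of Dosing Period 1, and SAP 10.2 has no classification rule for an AE dated to a dosing day with its onset time missing

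*SAP*

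**What the plan says.** **Medications (SAP 6.3).** A concomitant medication belongs to Dosing Period 1 when "the start or end date is on or after IMP administration in Dosing Period 1 and prior to IMP administration in Dosing Period 2". It belongs to Period 2 when either date is on or after the second dose. If the stop date is completely unknown, it is left blank and the medication goes to every Dosing Period after its start. A stop date known only to the month is set to the last day of that month. Concomitant medications are tabulated by treatment.

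**Adverse events (SAP 10.2).** A TEAE is defined by start date and time relative to the first dose; a pre-treatment AE is defined by start date alone. For periods, "Adverse events will be assigned to Dosing Periods, based on the onset date/ time of the AE", and "Assignment to Dosing Periods will be done after missing dates have been imputed as described" in the text above. The two period definitions then speak of date only: "Dosing Period 1: the start date is on or after IMP administration in Dosing Period 1 and prior to IMP administration in Dosing Period 2", and "Dosing Period 2: the start date is on or after IMP administration in Dosing Period 2".

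The rules for incomplete start dates cover month-only, year-only and unknown dates. When a month-only start falls in the month of the first dose and is set to that date, "If the imputed date is the date of dosing then time will be imputed as the start time of the dosing", so that the event counts as treatment-emergent; the year-only rule does the same. A complete date without a time appears only in Table 10-1, where "Onset time is substituted by 00:00h". The table's stated purpose is: "Missing or partially missing date and/or times will be imputed as described in [Table 10-1](#) for the calculation of duration of each AE".

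**The concern.** The medication rule tests whether one of two dates lies inside a period, not whether the medication was in use during it. These differ for a medication that begins before the period and ends after it.

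For AEs, time decides the classification on exactly two days per participant: the two dosing days. Protocol section 9.4.1 leaves the attribution rules to the SAP, so a gap there is not filled in the protocol. TEAE incidence is the secondary endpoint and is reported by formulation. Median time to maximum concentration is 1 h (protocol section 2), so dosing days are when drug-related events are most likely. The paragraph on period assignment stands directly after Table 10-1 and points back to the rules above it. A programmer looking for a time to use would find only 00:00, which precedes any morning dose.

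**Working it through.** No figure in the plan is at issue, so the check applies the rules to each possible case. The doses are 7 to 10 days apart (SAP 1.2). I assume both are given at 09:00; any time after midnight gives the same result. Both ends of the interval were tried and agree.

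**Medications.** The literal rule is compared with an overlap rule: Period 1 if start < dose 2 and stop ≥ dose 1; Period 2 if stop ≥ dose 2.

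| Start | Stop | SAP 6.3 as written | Overlap |
|---|---|---|---|
| before dose 1 | before dose 1 | none | none |
| before dose 1 | between doses | Period 1 | Period 1 |
| between doses | between doses | Period 1 | Period 1 |
| between doses | after dose 2 | Periods 1 and 2 | Periods 1 and 2 |
| **before dose 1** | **after dose 2** | **Period 2 only** | **Periods 1 and 2** |
| after dose 2 | after dose 2 | Period 2 | Period 2 |

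Only the fifth pattern differs. It also arises by imputation. With doses on 5 and 12 April, a medication started on 2 April and recorded as stopped in April gets a stop date of 30 April and is counted in Period 2 only. With a completely unknown stop date, the same medication goes to both periods. Knowing more about the stop date should not remove Period 1.

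**AEs with a complete dosing-day date and no time.**

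| Onset date | 00:00 carried over | Date only | Dosing time used |
|---|---|---|---|
| dose 1 day | before the first dose, so not a TEAE | Period 1 | Period 1 |
| dose 2 day | Period 1 (other formulation) | Period 2 | Period 2 |

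Under the first reading, the dose 1 day event is not pre-treatment either, because that class needs a start date before the first dose. It falls in neither class. Under the other two readings nothing is misattributed. On non-dosing days the date settles the matter.

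**Size.** With the planned 24 participants each receiving both formulations, one participant is 1/24 = 4.2 percentage points of a by-treatment column. A dose 2 day event assigned to Period 1 can lower one column and raise the other by that amount.

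**The case against.** A reader might infer that the SAP sets every dosing-day AE without a time to 00:00, and so makes it pre-treatment or moves it to the wrong formulation. The documents do not support that. The 00:00 row belongs to a table of duration rules, where it gives an upper bound on duration. The assignment sentence speaks of missing dates, and an AE with a complete date has none. The period definitions use start date, and applied by date they place both dosing-day cases correctly. The pre-treatment label does not fit the SAP's definition at all. What stands is a gap: time governs classification, the text alternates between date and date/time, and nothing stops the duration rule from being carried over.

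Nor is the dosing-time convention universal. It applies when the incomplete date falls in the month or year of the first dose; otherwise the SAP itself uses 00:00. A month-only AE in the month after dose 1 is normally set to the 1st at 00:00, and goes to Period 1 even if dose 2 is in that month. The doses fall in different months for 12 × 7/365 = 23% to 12 × 10/365 = 33% of dose 1 dates, if these are uniform over the year. That is a stated convention for an unknown day, and a separate matter from this gap.

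On size, the objection is largely right. Participants are confined from Day -1 to Day 3, so missing onset times should be rare. Tables count unique participants, and 80.4% of BRV participants in the pooled Phase 1 data (mixed doses) had a TEAE, so one misplaced event may leave overall incidence unchanged. AE listings show dates as reported, so cases can be traced. Most concomitant medication is prohibited; medicines for external use, which exclusion criterion 8 exempts, and treatment of an AE are the likely exceptions. A spanning medication still appears in the overall summary and the listing. None of this makes the medication rule correct as written.

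**Conclusion.** The medication point holds on the literal text of SAP 6.3, for one pattern: start before dose 1 and a known or imputed stop after dose 2. Such a medication is missing from the Period 1 treatment's column.

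The AE point holds as an omission. SAP 10.2 does not say how to classify an AE with a known dosing-day date and no time, and it permits two readings with different results. Misattribution follows only if the duration rule is carried over.

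The impact is small and confined to the by-treatment medication and AE tables: at most 4.2 percentage points per affected participant in a column of 24, and for AEs only if he has no other TEAE in that cell. The number of such cases cannot be known from the documents; it should be low. The bioequivalence analysis is not affected. This is a desirable clarification, not a condition for the analysis to be valid.

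**What to change.** In SAP 6.3, replace the period rule with overlap:
- Period 1 if the medication started before dose 2 and stopped on or after dose 1, or is ongoing.
- Period 2 if it stopped on or after dose 2, or is ongoing.

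The boundary should be dose 2 and not the end of the Dosing Period. SAP Table 5-1 ends each Dosing Period at Day 3, so a period-end boundary would leave a medication taken only during wash-out, now assigned to Period 1, without any period.

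In SAP 10.2:
- State that the times substituted in Table 10-1 are for duration only.
- For an AE with a known dosing-day date and missing onset time, use that period's dosing time for TEAE status and period assignment, unless the event is known to have ended before the dose.
- Use one date/time basis for the TEAE, pre-treatment and Dosing Period definitions.

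The cost is a few sentences in the SAP and minor programming. No new data are needed.

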8.2.4 Physical examination

A complete physical examination will include, at a minimum, general appearance; ear, nose, and throat; eyes, hair, and skin; and assessments of the cardiovascular, respiratory, gastrointestinal, neurological, musculoskeletal, and hepatic systems. Height and weight will also be measured and recorded at screening only.

A brief physical examination will include, at a minimum, assessments of the skin, respiratory system, cardiovascular system, and abdomen (liver and spleen).

Investigators should pay special attention to clinical signs related to previous serious illnesses.

Clinically relevant findings or worsening of previous findings will be recorded as AEs.

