10.3 Appendix 3: Adverse Events – Definitions and Procedures for Recording, Evaluating, Follow up, and Reporting

Definition of AE

AE Definition

- An AE is any untoward medical occurrence in a patient or clinical study participant, temporally associated with the use of IMP, whether or not considered related to the IMP.
- NOTE: An AE can therefore be any unfavorable and unintended sign (including an abnormal laboratory finding), symptom, or disease (new or exacerbated) temporally associated with the use of IMP.

Events Meeting the AE Definition

- Any abnormal laboratory test results (hematology, clinical chemistry, or urinalysis) or other safety assessments (eg, ECG, radiological scans, vital signs measurements), including those that worsen from Baseline, considered clinically significant in the medical and scientific judgment of the Investigator (ie, not related to progression of underlying disease).
- Exacerbation of a chronic or intermittent pre-existing condition including either an increase in frequency and/or intensity of the condition.
- New conditions detected or diagnosed after IMP administration even though it may have been present before the start of the study.
- Signs, symptoms, or the clinical sequelae of a suspected drug-drug interaction.
- Signs, symptoms, or the clinical sequelae of a suspected overdose of either IMP or a concomitant medication. Overdose per se will not be reported as an AE/SAE unless it is an intentional overdose taken with possible suicidal/self-harming intent. Such overdoses should be reported regardless of sequelae.

Events NOT Meeting the AE Definition

- Any clinically significant abnormal laboratory findings or other abnormal safety assessments, which are associated with the underlying disease, unless judged by the Investigator to be more severe than expected for the study participant's condition.
- The disease/disorder being studied or expected progression, signs, or symptoms of the disease/disorder being studied, unless more severe than expected for the study participant's condition.
- Medical or surgical procedure (eg, endoscopy, appendectomy): the condition that leads to the procedure is the AE.
- Situations in which an untoward medical occurrence did not occur (social and/or convenience admission to a hospital).
- Anticipated day-to-day fluctuations of pre-existing disease(s) or condition(s) present or detected at the start of the study that do not worsen.

Definition of SAE

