- An AE should be followed until it has resolved, has a stable sequelae, the Investigator determines that it is no longer clinically significant, or the study participant is lost to follow up. This follow-up requirement applies to AEs, SAEs, and AEs of special interest.
- New or updated information will be recorded in the originally completed CRF.
- The Investigator will submit any updated SAE data to UCB within 24 hours of receipt of the information.

Reporting of SAEs

SAE Reporting to UCB via Paper CRF

- The primary mechanism for reporting an SAE to UCB will be the paper SAE data collection tool.
- Facsimile transmission of the sop-af-004166 SAE Report Form for Development Product is the preferred method to transmit this information to UCB Drug Safety.
- In rare circumstances and in the absence of facsimile equipment, notification by telephone is acceptable with a copy of the SAE data collection tool sent by overnight mail or courier service.
- Initial notification via telephone does not replace the need for the Investigator to complete and sign the SAE CRF pages within the designated reporting time frames.
- Contacts for SAE reporting can be found in the **SERIOUS ADVERSE EVENT REPORTING** section at the front of the protocol.

This document cannot be used to support any marketing authorization application and any extensions or variations thereof.
PUBLIC COPY

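### SAP 10.2 assigns adverse events to a formulation by onset alone, so a TEAE that began before Day 1 of Dosing Period 1 and qualifies only by worsening can belong to neither tablet nor dry syrup

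*SAP*

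**What the plan says.** Protocol 9.4.1 defines pretreatment AEs and TEAEs and leaves the rules for attributing AEs to a Dosing Period to the SAP. SAP 10.2 supplies them.

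- **TEAE.** Besides events starting on or after the first dose, the definition covers "any unresolved event already present before administration of IMP that worsens in intensity following exposure to IMP".
- **Pre-treatment AE.** "Adverse events with a start date prior to the first dose of IMP will be defined as pre-treatment AEs". No exception is made for an event that later worsens. Protocol 9.4.1 has the same overlap.
- **Attribution.** "Adverse events will be assigned to Dosing Periods, based on the onset date/ time of the AE". Treatment then follows from the Dosing Period. For Dosing Period 1 the condition is "the start date is on or after IMP administration in Dosing Period 1 and prior to IMP administration in Dosing Period 2". The other rule reads "Dosing Period 2: the start date is on or after IMP administration in Dosing Period 2".

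SAP 10.2.1 tabulates TEAEs and treatment-emergent SAEs, the secondary endpoints, by formulation and overall. SAP 10.2.2 adds a separate summary of AEs that occurred before the first dose, and a listing of all AEs by sequence, period and treatment in which TEAEs are flagged.

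**The concern.** The definition admits a class of TEAE that the attribution rule cannot place. An event that starts during screening and worsens after dosing is treatment-emergent because of what happened after IMP, but the rule looks at when it began. The date of worsening is used nowhere.

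At stake is the internal consistency of the by-formulation safety tables. The overall column could hold a participant whom neither formulation column holds, and one event could be both pre-treatment and treatment-emergent. The study compares two formulations, so the formulation to which a TEAE belongs should be fixed in advance. The SAP does deal with the parallel case for medications. SAP 6.3 assigns them to periods by start or end date, and SAP 11.1.4 states that one spanning the dose is both prior and concomitant. AEs have no equivalent.

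**Working it through.** The plan gives no figure to reproduce here. The check is one of logic, followed by a bound on size.

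**Inputs.** The definitions and period rules are from SAP 10.2. Protocol 8.3.1 starts AE collection at consent, and screening runs from 28 to 2 days before IMP, so pre-dose onsets can be in the database. The planned number is 24 (SAP 3).

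**Rules in symbols.** Let s be onset, w the time of worsening, and d1 and d2 the two administrations, with d1 < d2.

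- TEAE: s ≥ d1, or the event is unresolved with s < d1 and w ≥ d1.
- Pre-treatment: s < d1.
- Dosing Period 1: d1 ≤ s < d2. Dosing Period 2: s ≥ d2.

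If s < d1, neither period condition can hold, whatever w is.

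| Pattern | TEAE | Pre-treatment | Period assigned |
|---|---|---|---|
| Onset before dose 1, no worsening | no | yes | none |
| Onset before dose 1, worsens after dose 1 | yes | yes | **none** |
| Onset before dose 1, worsens only after dose 2 | yes | yes | **none** |
| Onset in Period 1 | yes | no | 1 |
| Onset in Period 1, worsens after dose 2 | yes | no | 1 |
| Onset in Period 2 | yes | no | 2 |

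Rows two and three are the gap.

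**Does another rule close it?**

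- *Imputation (SAP 10.2)* acts on partial or unknown start dates. A known pre-dose onset stays where it is.
- *Table 5-1 (SAP 5.1.1.1.3)* opens Dosing Period 1 at Day -1. At most that would reach Day -1 onsets, and it conflicts with the specific AE rule. Day -28 to Day -2 is the Screening Period.
- *SAP 5.1.1.3* uses the treatment actually received in each Dosing Period, which presupposes that a period has been assigned.
- *Day 1, before dosing.* The lead sentence of the rule refers to date and time, but the two period conditions refer to the start date. On a date-only reading, a Day 1 predose onset goes to Period 1; on a date-and-time reading it goes nowhere. The gap is certain only for onsets before Day 1.

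**Size.** With N = 24 on each formulation, one unassigned participant changes that formulation's incidence of any TEAE by 1/24 = 4.2 percentage points if he has no other TEAE on it, and by 0 if he has. The same bound applies to treatment-emergent SAEs.

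**The case against.** The strongest objection is that the gap depends on how worsening is recorded. If it is entered as a new AE with its own onset, the onset rule works. Some of the protocol leans that way. Section 8.2.4 says "Clinically relevant findings or worsening of previous findings will be recorded as AEs"; Section 10.3 (Appendix 3) counts as an AE "Exacerbation of a chronic or intermittent pre-existing condition including either an increase in frequency and/or intensity of the condition"; and Section 8.3.1 makes AEs that worsened after the initial visit reportable. None of these tells the site to open a new record or set a new onset, and Appendix 3 also says "New or updated information will be recorded in the originally completed CRF". Protocol 10.1.5.1 refers detailed instructions to the CRF Completion Guidelines. Neither these nor eCRF v2.0 is available here. The objection therefore stands as a condition on the finding and does not refute it.

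Several stronger readings are tempting, and the documents do not support them:

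- *The event disappears from the report.* The AE listing in SAP 10.2.2 would show it flagged as a TEAE, and the overall column would presumably count it, although the SAP does not say how that column is built. Its place in the summary of AEs before the first dose is not wrong in itself, since it did begin then.
- *The table of non-serious TEAEs above 5% is in real danger.* Arithmetically, 2/24 = 8.3% is shown and 1/24 = 4.2% is not. Losing a preferred term this way needs exactly two participants with the same term on one formulation, one of them unassigned. Nothing suggests that this is likely.
- *The full 4.2 points is the expected effect.* It is a maximum. In the pooled Phase 1 data in Protocol Section 2, 586 of 729 BRV participants (80.4%) had a TEAE. That pool is not limited to the present dose or formulations, so it is only a guide, but the more participants have another TEAE, the more often the effect on any-TEAE incidence is zero.
- *Open-label review would bias attribution.* Once the date of worsening is known, the period is known too, so little discretion remains. Bias at the Data Evaluation Meeting would be speculation.

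**Conclusion.** The point holds in a limited form. If worsening stays on the original AE record, SAP 10.2 gives no formulation to a TEAE with a known onset before Day 1 of Dosing Period 1, and the same event also falls under the pre-treatment definition. The by-formulation TEAE and treatment-emergent SAE tables would omit it. A Day 1 predose onset depends on which wording of the rule governs.

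The number of such events cannot be estimated from the documents. It should be very small or zero: participants are healthy, the window runs only from consent to the first dose, and eligibility is verified again on Day -1. The summaries are descriptive, and the Cmax and AUC(0-t) assessment is untouched. Severity is low, but the rule as stated misplaces an event in a secondary endpoint and is easily corrected.

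**What to change.** In SAP 10.2:

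1. Assign a TEAE that qualifies only because a pre-first-dose event worsened to the Dosing Period, and hence the treatment, in which it worsened. Use the date and time of worsening, or a new AE record with that onset. State that AEs starting on or after the first dose stay assigned by onset, so that the boundary between the two principles is explicit.
2. Exclude such events from the pre-treatment category so that the two categories do not overlap. Record this in SAP 11.2, which now lists no changes, because Protocol 9.4.1 carries the same definition.

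The cost is a few sentences, one entry in SAP 11.2 and minor programming. The downside is a dependence on data capture: eCRF v2.0 and the CRF Completion Guidelines must be checked to see that they hold the date of worsening or require a new record. If a new record is already required, the change only confirms practice.
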